## Study Design

This is a single-site, prospective, interventional, twenty-four week, randomized, double blind, placebo-controlled trial with bromocriptine QR in subjects with early diabetes and established T2DM to evaluate its effects on the cardiovascular and peripheral autonomic nervous system, as well as inflammatory markers, the leptin/adiponectin system, hormonal levels of RAS and HPA axis, indices of insulin resistance and glycemic control, and measures of oxidative and nitrosative stress. At least twenty (20) but no more than forty (40) early diabetes subjects and at least forty (40) but no more than sixty (60) subjects with established diabetes will be enrolled in the study.

Entry criteria will be checked at the screening visit. Subjects will be required to be on a stable anti-diabetes regimen consisting of diet and/or oral anti-diabetic agents consisting of metformin alone or metformin plus an insulin secretion enhancer (sulfonylurea, DPP4 Inhibitors, or GLP-1 analogs) for at least 60 days prior to randomization. Following a 2 week lead-in period, subjects will be randomized in a 1:1 ratio to receive UDT (usual diabetes therapy) plus bromocriptine-QR or UDT plus placebo. The circadian timing of the interventional therapy will be within 2 hours of waking in the morning.

Following randomization, subjects will be titrated to the maximum tolerated dose of the study drug (bromocriptine-QR or placebo) over a 4 week period.

Subjects will return at 4 weeks after randomization, at 12 weeks after randomization, and then at study end (week 24 or early termination) for analyses of the primary and secondary endpoints. A primary analysis of the study data will be performed after 12 weeks with a secondary analysis conducted at 24 weeks. Subjects will be contacted 30 days after stopping the study drug to record any adverse events that occurred after cessation.

All visits will be conducted at The Strelitz Diabetes Center, Norfolk, VA.

---

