metformin alone or metformin plus an insulin secretion enhancer (sulfonylurea, DPP4 Inhibitors, or GLP-1 analogs) for at least 60 days prior to randomization. Following a 2 week lead-in period, subjects will be randomized in a 1:1 ratio to receive UDT (usual diabetes therapy) plus bromocriptine-QR or UDT plus placebo. Subjects must have a documented C-peptide level of >2 ng/ml from the screening visit. The circadian timing of the interventional therapy will be within 2 hours of waking in the morning. Following randomization subjects will be titrated to the maximum tolerated dose of the study drug over a four-week period. During these first 4 weeks, the daily dose of the study drug will be titrated up by one tablet (0.8 mg bromocriptine-QR or 1 matching placebo tablet) per day on a weekly basis until a maximal tolerated dose of at least two tablets (1.6 mg/day bromocriptine-QR or 2 placebo tablets) and no more than four tablets (3.2 mg/per day b-QR or 4 placebo tablets) is achieved. During the first 4 weeks of the study, subjects will be called weekly to monitor for possible adverse events. Subjects will be maintained at their maximum tolerated dose of between two to four tablets per day (1.6 to 3.2 mg bromocriptine-QR per day or 2 to 4 placebo tablets) for the duration of the study. Subjects unable to tolerate two tablets per day of study drug will be terminated from the study and any further analyses. Subjects will be seen at 4 weeks after randomization, at 12 weeks after randomization, and then at study end (week 24 or early termination). A primary analysis of the primary and secondary endpoints will be performed after 12 weeks with a secondary analysis conducted on these study endpoints at 24 weeks. Subjects will be contacted 30 days after stopping the study drug to record any adverse events that occurred after cessation. During the study period subjects will be advised to perform home blood glucose monitoring at least on a daily basis. Subjects will be required to continue their usual anti-diabetes regimen during the study but will be allowed to alter the dosages of these medications and/or add or subtract medications as deemed necessary by the Principal Investigator to optimize blood glucose control to avoid hypoglycemia or persistent hyperglycemia. In any case, rescue therapy for hyperglycemia will be administered if a subject has two consecutive fasting glucose measurements >270 mg/dL spaced  $\leq 7$  days apart before week 12, or two consecutive fasting glucose measurements >250 mg/dL spaced  $\leq 7$  days apart or a HbA1c >11% at or after week 12. The choice of rescue therapy will be at the discretion of the Principal Investigator and may include adjustments in the dosages of the medications that the subject is already on and/or addition of other glucose lowering therapies. The subjects with concurrent antidiabetes medication changes may remain "on study" for the remainder of the study until week 24 undergoing all evaluations if in the opinion of the investigator this does not pose any serious risk to the subject or the study objectives unless the rescue therapy requires insulin, in which case the subject will be withdrawn from the study as per the exclusion criteria for the study. Subjects will receive a complete physical and neurological exam and clinical laboratory assessments at baseline and at the completion of the study. The primary and secondary endpoints will be evaluated at baseline, week 4, week 12, and week 24 or at early termination. Subjects will be evaluated using the procedures listed below.

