## **7.3 STATISTICAL METHODS**

Statistical analyses will be conducted on between group (bromocriptine-QR vs. placebo) differences in change from baseline of all primary and secondary endpoints. The treatment effects on all of the primary and secondary outcomes will also be assessed as a function of the duration of diabetes and other baseline demographics such as HbA1c, concomitant medications and metabolic status. Mean differences of glycemic control, various derivative autonomic function values, and inflammatory marker levels will be compared first using standard Analysis of Variance (ANOVA), with diagnostic group entered as the predictor variable. Within-group analysis for change in primary and secondary endpoints after 12 weeks of treatment will be done using repeated measures MANOVA (multivariate analysis of variance). For glycemic control analysis patients will be stratified according to post-prandial insulin response. If data are not normally distributed, the Wilcoxon signed-rank (within group) or Mann Whitney (between group) tests may be employed or Fisher's exact test in case of small sample sizes. The level of significance will be set at  $p < 0.05$ . Relationships and/or trends between the effect of Cycloset on neurovascular function and diabetic neuropathy will be determined with Spearman's rank correlation.

A statistical analysis plan (SAP), providing details of the analyses and presentation structure of the results, will be developed and finalized before the database is locked.

A local laboratory will be utilized for collection and analysis of the laboratory tests associated with efficacy, and safety. Standardized guidelines for preparation, collection, and centralized analysis of blood specimens will provide uniformity of the data and will avoid potential inter-laboratory variability due to inconsistent methodology.

The analyses of plasma markers of inflammation, oxidative/nitrosative stress, neuroendocrine factors, and the adiponectin/leptin ratio will be conducted at VeroScience (Tiverton, RI).

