## 9.6 ANALYSIS POPULATIONS

The primary analysis of the study will be the assessment of the primary and secondary study endpoints after 12 weeks of study drug treatment. The secondary analysis of the study will be the assessment of the primary and secondary study endpoints after 24 weeks of study drug treatment.

Dropouts will be replaced as described in section 9.1.

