Impact of Timed Bromocriptine-QR Therapy upon Measures of Sympathetic Tone and Vascular Biology in Type 2 Diabetes Subjects

Statistical Analysis Plan

Date: Dec 14, 2018

Study Objectives:

Primary Objective:

To demonstrate the effects of dopaminergic activation with bromocriptine-QR on the autonomic nervous system in subjects with type 2 diabetes.

Secondary Objectives:

The Co-secondary objectives of the study were the following:

- 1) To assess the impact of bromocriptine-QR vs placebo on measures of insulin resistance and glycemic control
- 2) To demonstrate the effects of dopaminergic activation with bromocriptine-QR on the regulation of plasma neuroendocrine factors such as the hypothalamic-pituitary-axis (HPA) hormones, and on the plasma levels of markers of inflammation and oxidative/nitrosative stress in type 2 diabetes subjects.

Study Endpoints and Analysis Plan

Primary Endpoint

Changes in autonomic function measures from baseline to week 24 following treatment with study drug (bromocriptine-QR or placebo).

The effect of treatment with study drug for 24 weeks on the following three measures of autonomic function will be analyzed:

- 1) Heart Rate Variability
- 2) Resting Heart Rate
- 3) Sudorimetry

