Between treatment group differences in the change from baseline to week 24 in the above autonomic function parameters will be analyzed. All analyses will be stratified by baseline resting heart rate (RHR) ≥ 70 or < 70 beats per min (BPM) (see below). The rationale for such stratification is as follows. Elevated RHR is known to be a simple and useful clinical measure of elevated sympathetic nervous system activity as it reflects central sympathetic-parasympathetic activity balance^{1,2} and has been shown to correlate with other measures of SNS activity such as muscle sympathetic nerve activity and serum noradrenalin levels and heart rate variability³⁻⁶. While clinically, RHR between 60-100 BPM is considered the “normal” range for RHR and RHR ≥ 100 is used as the criteria for defining tachycardia, a large body of evidence from epidemiological and clinical studies suggest that increasing RHR even within the “normal” range is associated with increased cardiometabolic risk, particularly above around 70, likely reflecting the deleterious effects of underlying elevated sympathetic tone leading to such elevated RHR. Such elevated RHR has been associated with insulin resistance^{7,8}, altered beta cell function⁹, impaired glucose regulation and increased risk of developing type 2 diabetes mellitus¹⁰⁻¹² as well as increased cardiovascular risk¹³⁻³¹ and mortality^{13-23,26,27,29,31-40}. In addition to and consistent with the reported evidence supporting elevated RHR threshold of approximately 70 BPM as an indicator of elevated sympathetic tone, a previous study that evaluated the effect of bromocriptine-QR on RHR in subjects with type 2 diabetes demonstrated that bromocriptine-QR’s influence to reduce RHR is only observable if the RHR is elevated to ≥ 70 BPM and the magnitude of this reduction was greater the more elevated the baseline RHR was above 70 BPM with greater reductions seen with baseline RHR ≥ 80 ^{41,42}. Furthermore, it was observed that the degree of

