Between treatment group differences in the change from baseline to week 24 in the levels of the above factors will be analyzed in the overall cohort as well as with stratification by baseline RHR ($< \geq 70$ BPM) as described above for the analysis of autonomic function markers as well as stratification by baseline HbA1c ($< \geq 7.0$) as described above for the analysis of glycemic control parameters.

Statistical Methods:

Between treatment group (bromocriptine-QR vs. placebo) differences in change from baseline to week 24 and within group changes from baseline to week 24 of all primary and secondary endpoints will be analyzed using Independent Samples T-tests. If the data are not normally distributed in raw form or in some cases after simple log transformation, then appropriate non-parametric tests will be used instead. Within group analyses will be performed using paired samples T-test or repeated measures ANOVA as appropriate. The treatment effects on the primary and secondary outcomes will also be assessed after adjustment as needed for other potential factors that could influence the specific endpoint being analyzed such as duration of diabetes, baseline HbA1c, baseline RHR and/or change in RHR from baseline, concomitant medications and other baseline demographics as appropriate using categorical stratified analyses as discussed above and/or multivariable regression analyses methods.

References:

4. Egan BM: Insulin resistance and the sympathetic nervous system. *Curr Hypertens Rep* 2003;5:247-254

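### The SAP swaps the protocol's primary time point (week 12) for its secondary one (week 24) and leaves out the laser component of the primary endpoint, explaining neither

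*SAP*

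**What the plan says.** **Protocol, time point.** Section 9.6 states: "The primary analysis of the study will be the assessment of the primary and secondary study endpoints after 12 weeks of study drug treatment". Its next sentence reads: "The secondary analysis of the study will be the assessment of the primary and secondary study endpoints after 24 weeks of study drug treatment". The Study Design entry of the Protocol Outline agrees ("A primary analysis of the study data will be performed after 12 weeks with a secondary analysis conducted at 24 weeks"), and so does section 3.1 ("A primary analysis of the primary and secondary endpoints will be performed after 12 weeks with a secondary analysis"). Section 7.3 sets the type of comparison: "Statistical analyses will be conducted on between group (bromocriptine-QR vs. placebo) differences in change from baseline of all primary and secondary endpoints".

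**Protocol, components.** The Study Endpoints entry of the outline, section 2.1 and section 7.3.1 describe the primary endpoint in the same way. It is autonomic function by conventional measures, including power spectral analysis of heart rate, together with sudorimetry and laser scanning of peripheral microvascular control.

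**SAP.** The Primary Endpoint section gives the endpoint as "Changes in autonomic function measures from baseline to week 24 following treatment with study drug (bromocriptine-QR or placebo" and lists three measures: heart rate variability, resting heart rate and sudorimetry. It continues: "Between treatment group differences in the change from baseline to week 24 in the above autonomic function parameters will be analyzed". The Statistical Methods section extends the same time point to "differences in change from baseline to week 24 and within group changes from baseline to week 24 of all primary and secondary endpoints".

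**The concern.** The two governing documents define different primary results for one trial. An analyst working from the SAP alone would produce no week-12 between-arm result, which is the protocol's primary analysis, and no result for one component the protocol names as primary. Two reports could then each claim a different primary finding from the same data.

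The choice of time point can matter. Section 3.1 allows background diabetes medication to change during the study, and subjects may leave between weeks 12 and 24. The two comparisons can therefore differ in both treatment context and subjects.

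The SAP argues at length for its resting-heart-rate strata and gives reasons for its glycemic choices. It says nothing about why the primary time moved or where the laser measure went.

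**Working it through.** The point is a comparison of texts. The plan's only related figure, 80 participants for power above 0.80 (section 9.7), cannot be reproduced because no standard deviation is given. It is tied to neither time point nor to any one component, so it does not settle which definition was intended.

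**Step 1: the two documents side by side.**

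| Item | Protocol | SAP |
|---|---|---|
| Week 12 | Primary analysis (3 places) | Not named |
| Week 24 | Secondary analysis | The only analysis time named |
| Heart rate | Power spectral analysis named | Heart rate variability; outputs not specified |
| Sudorimetry | Named | Named |
| Laser measure | Named in the primary endpoint (3 places) | Absent from primary and secondary endpoints |
| Resting heart rate | Not listed as an endpoint | Listed as primary |

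**Step 2: mentions in the SAP text before its references.** Week 24 appears 8 times, and 24 weeks (with or without a hyphen) twice: 8 + 2 = 10. Week 12 appears 0 times. Laser or skin blood flow appears 0 times.

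**Step 3: coverage.** The protocol gives two times the rank of an analysis, weeks 12 and 24. Week 4 is a measurement visit without that rank. The SAP names 1 of 2 for heart rate variability and sudorimetry, and 0 of 2 for the laser measure. Of the three named components, one is plainly kept (sudorimetry), one appears under a broader label, and one is missing. The broader label matters because section 3.1 places both spectral power and time-domain outputs (sdNN, rmSSD) under heart rate variability.

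**Step 4: was week 12 measured?** Yes. The Study Schedule and section 7.2.2.7 place autonomic tests, sudorimetry and skin blood flow at week 12. Which laser output exists is less clear. Section 3.1 describes both continuous laser Doppler and a scanning imager, while all four visit lists (7.2.2.1, 7.2.2.5, 7.2.2.7, 7.2.2.10) name only the continuous method.

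**Step 5: the SAP date against the planned end of the study.** There are two readings.

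- The outline plans for the last subject to finish by August 2018. From 31 August to 14 December 2018 is 30 + 31 + 30 + 14 = 105 days; from 1 August it is 105 + 30 = 135 days. On this reading the SAP comes 105 to 135 days after the last visit.
- Section 3.2 can be read as recruitment ending by August 2018. Assume a last randomisation between 1 and 31 August. Adding 24 × 7 = 168 days gives 16 January to 15 February 2019. From 14 December that is 17 + 16 = 33 to 17 + 31 + 15 = 63 days. On this reading the SAP comes 33 to 63 days before the last week-24 visit.

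The 38 months in section 3.2 fit August 2018 as the end of the study (July 2015 to August 2018 inclusive: 6 + 12 + 12 + 8 = 38), which favours the first reading. The same section says that actual dates may vary. Neither document gives the actual last visit, the lock date or the blinding status on the SAP date.

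**The case against.** Five things can be said for the SAP.

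- **Week 24 is not new.** The protocol planned it for the same endpoints, and its endpoint definitions carry no time. This stands: the change is one of rank between two planned analyses.
- **The SAP does not cancel week 12.** A reader might infer that the protocol's primary analysis was abandoned. The text does not support that: the SAP is silent on week 12 and does not claim to supersede the protocol. Its optional within-group repeated measures ANOVA could draw on intermediate visits. However, it names no week-12 contrast and is not a between-arm test, so it does not fill the gap.
- **The protocol leaves detail to the SAP, and its wording is open.** The word *including* can admit resting heart rate. It does not explain removing an item that is named, and reversing primary and secondary goes beyond detail. Section 10.5 treats changes to the protocol as needing written agreement.
- **Nothing shows a breach of blinding.** A reader might infer from the December 2018 date that week 24 was chosen after results were seen. The documents do not support that. The code envelope is to stay sealed until the study is concluded, the SAP is to be final before database lock, and the dates can be read either way. No amendment on this point is in the material supplied, but that material is not complete, so its absence carries little weight.
- **No effect on the result is shown.** This stands. The point concerns which result is primary, not how far any estimate moves.

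**Conclusion.** The conflict holds and must be resolved. The protocol ranks week 12 first in three places; the SAP names only week 24. One of the protocol's three named primary components, the laser measure, is missing from the SAP. A second, spectral analysis, is not clearly retained. Resting heart rate is added. No reason is given for the time point or for the laser omission.

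On the documents as they stand, week 24 cannot be reported as the protocol's primary result. The conclusion rests on the text alone and needs no assumption about dates, blinding or effect size. Whether the swap preceded lock or was made blind remains unknown.

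**What to change.** Reconcile the two documents in one of two ways.

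(a) Make the SAP follow the protocol. The between-arm comparison of change from baseline to week 12 is primary and week 24 is secondary. Include the laser measure that was recorded, and state whether it is imaging or continuous laser Doppler.

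(b) Keep week 24 through a dated amendment that gives the reason and the lock and blinding status at that date. Report the week-12 between-arm analysis of the protocol's named measures alongside it, labelled as the protocol's primary analysis.

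In either case, label resting heart rate as added by the SAP and state which heart rate variability outputs are analysed.

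The cost is SAP wording and a little more analysis. The measurements are already scheduled at week 12, so no visit or test is added. The downside is that week 24 is no longer the sole headline result. If only continuous laser Doppler was recorded, the SAP must say that it stands in for laser scanning.

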## Study Endpoints

The primary endpoint is the effect of bromocriptine-QR vs placebo on changes in autonomic function measured by assessing sympathetic and parasympathetic function using conventional measures of autonomic function, including power spectral analysis of heart rate as well as peripheral autonomic function using sudorimetry and laser scanning of peripheral microvascular autonomic control.

Secondary endpoints will be bromocriptine-QR vs placebo effects on inflammatory markers, markers of oxidative/nitrosative stress, the leptin/adiponectin system, and hormonal levels of the renin-angiotensin system (RAS), aldosterone and cortisol. The following plasma markers of inflammation and oxidative/nitrosative stress will be evaluated: 1) CRP, 2) IL6,3) TNF  $\alpha$ , 4) PAI1, SOD, TBARS and ADMA will be assessed as well as nitrotyrosine and other markers of oxidative/nitrosative stress .

---

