### 7.3.1 **Primary endpoint**

The primary endpoint is the effect of bromocriptine-QR on changes in autonomic function measured by assessing sympathetic and parasympathetic function using conventional measures of autonomic function, including power spectral analysis of heart rate as well as peripheral autonomic function using sudorimetry and laser scanning of peripheral microvascular autonomic control.

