bromocriptine-QR's impact to reduce elevated RHR was an independent predictor of its effect to reduce HbA1c among subjects with poor glycemic control (baseline HbA1c ≥ 7.5)⁴¹. The rationale for the categorical stratification of ≥ 70 or < 70 BPM for the analysis of the data from this current study is therefore based on the above considerations. A subset analysis will also be conducted in subjects with baseline RHR ≥ 80 BPM. We hypothesize that the treatment effect on SNS will be expressed in the RHR ≥ 70 BPM group.

Secondary Endpoints:

1) Measures of insulin resistance and glycemic control

Given the mechanism of action of Cycloset to improve postprandial insulin sensitivity, the main endpoint that will be evaluated is the effect of study drug treatment on postprandial glycemic control based on the OGTT plasma glucose and insulin data obtained at baseline and week 24. Between treatment group differences in change from baseline to week 24 for the area under the curve as well as levels at different time points of OGTT plasma glucose and insulin levels will be analyzed. Matsuda index of insulin sensitivity calculated using the OGTT glucose and insulin levels and HOMA-IR calculated from fasting glucose and insulin levels will also be analyzed as measures of insulin sensitivity/resistance.

All subjects completing 24-weeks of study drug treatment with data for baseline and week 24 OGTT will be included in the analyses of glycemic endpoints. The analyses will be done in the entire cohort of subjects with and without stratification by baseline HbA1c level of < 7.0 and ≥ 7.0 (i.e. suboptimal glycemic control).

Given that as a postprandial insulin sensitizer, the presence of adequate postprandial insulin levels is an important determinant of the postprandial glucose lowering efficacy, further subset analyses will be conducted to assess the above endpoints in subjects with OGTT insulin at T60 mins ≥ 50 $\mu\text{U/ml}$ and also in the subset on an insulin secretory agent (+/- TZD). An analysis stratified by duration of diabetes (≤ 4 years or > 4 years) may also be conducted depending on sample size.

2) Measures of inflammation, oxidative/nitrosative stress and plasma neuroendocrine factors

The following plasma factors will be evaluated: cortisol, aldosterone, norepinephrine, normetanephrine, adiponectin, leptin, IL6, TNF α , PAI1, SOD, TBARS, ADMA, nitrotyrosine and other appropriate factors of increased systemic inflammation and reactive oxygen species.

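### The SAP's primary endpoint is three unranked measures with no success rule or multiplicity control, its time point and measure list depart from the protocol's, and the role of the heart-rate strata is left open

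*SAP*

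**What the plan says.** **SAP, Primary Endpoint.** The endpoint is change from baseline to week 24: "The effect of treatment with study drug for 24 weeks on the following three measures of autonomic function will be analyzed". The list is HRV, RHR and sudorimetry, with no order. On strata it says "All analyses will be stratified by baseline resting heart rate (RHR", with the cut at 70 beats per minute and a further subset at 80 or above. It then predicts: "We hypothesize that the treatment effect on SNS will be expressed in the RHR ≥ 70 BPM group".

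**SAP, Secondary Endpoints and Statistical Methods.** The plasma factors "will be analyzed in the overall cohort as well as with stratification by baseline RHR". The primary section has no matching mention of an overall cohort. The methods are independent-samples t-tests with a non-parametric fallback. Adjustment, as needed, is by "using categorical stratified analyses as discussed above and/or multivariable regression analyses methods". The SAP states no significance level, multiplicity procedure or treatment-by-RHR term.

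**Protocol.** Section 7.3.1 describes conventional autonomic measures, including "power spectral analysis of heart rate as well as peripheral autonomic function using sudorimetry and laser scanning of peripheral microvascular autonomic control". The Outline (Study Endpoints) and section 2.1 also name laser scanning. On timing, the Outline (Study Design) says: "A primary analysis of the study data will be performed after 12 weeks with a secondary analysis conducted at 24 weeks". Sections 3.1 and 9.6 agree. Section 7.3 describes a between-group comparison of changes from baseline at p < 0.05, with no RHR strata. Section 3.1 (Autonomic function tests) offers several HRV quantities: total spectral power in each of four test phases, sdNN and rmSSD.

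**The concern.** The stated aim is to demonstrate an effect on the autonomic nervous system, and the protocol claims power above 0.80 for it. A demonstration needs a rule fixed in advance: which result, at which week, in which subjects, counts as success. Here several results could each be reported as the primary finding, and nothing in the plan ranks them.

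Two consequences follow. First, the chance of a false primary claim depends on a rule that nobody has written down. Second, protocol and SAP would give different primary results from the same data: one at week 12 with laser scanning, the other at week 24 without it. The protocol lets the SAP supply analysis details before database lock. Moving the primary time point and dropping a named primary measure go beyond detail and need a recorded reason.

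**Working it through.** **1. The two documents side by side**

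| Item | Protocol | SAP |
|---|---|---|
| Primary time point | Week 12; week 24 secondary (Outline, 3.1, 9.6) | Week 24 |
| HRV | Power spectral analysis named; several indices and phases in 3.1 | HRV, no index or phase |
| Sudorimetry | Named | Named |
| Laser scanning | Named (Outline, 2.1, 7.3.1) | Absent from the primary list |
| Resting heart rate | Not named; the wording is open-ended | Named |
| RHR strata | None | All primary analyses, cut at 70 |
| Success rule, multiplicity control | None; p < 0.05 only | None; no level stated |

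**2. False-positive rate under each possible rule**

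Inputs: three measures (SAP) and 0.05 (Protocol 7.3), taken as two-sided because sidedness is not stated. The documents give no correlation between measures, so 0 to 0.7 is assumed, with 0.9 as a check. Strata contain different subjects, so their tests are independent.

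- Any one of three, one population, correlation 0: 1 − 0.95³ = 0.143. Simulation with equal correlations gives 0.142, 0.125 and 0.109 at 0, 0.5 and 0.7.
- Any one of three in either stratum: 1 − (1 − 0.143)² = 0.265 at correlation 0, and 1 − (1 − 0.109)² = 0.206 at 0.7.
- All three, one population: 0.05³ = 0.0001 at correlation 0. Simulation gives 0.003, 0.009 and about 0.02 at 0.5, 0.7 and 0.9.

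These are two-sided rates. Counting only hits in the favourable direction, any one of three gives 0.073 to 0.054.

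**3. What multiplicity control costs**

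The plan's own figure is power above 0.80 with about 40 per arm for a 10% change (Protocol 9.7). No SD is given and the measure is not named, so it cannot be reproduced. Solving backwards, a two-sided t-test with 40 per arm has power 0.80 at a standardised difference d = 0.634. For a 10-point difference that means an SD of 10 / 0.634 = 15.8 points. I use d = 0.634 as an illustration only.

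Holm's first step over three measures uses 0.05 / 3 = 0.0167, where power at d = 0.634 is 0.65. With four measures (0.0125) it is 0.61.

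**4. What a treatment-by-RHR estimate can show**

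Suppose d = 0.634 exists only at RHR ≥ 70, and the share of subjects there is 1/2, 2/3 or 3/4 (assumed). In SD units, the standard error of the difference between stratum effects is √(2/n₁ + 2/n₂), with n₁ and n₂ subjects per arm in the two strata.

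- Share 1/2: √(2/20 + 2/20) = 0.447; power about 0.29.
- Share 2/3: √(2/26.7 + 2/13.3) = 0.474; power about 0.26.
- Share 3/4: √(2/30 + 2/10) = 0.516; power about 0.23.

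Comparing stratum p-values is no substitute. With the same d = 0.634 in both strata, the probability of significance at ≥ 70 but not below is power(≥ 70) × [1 − power(< 70)]:

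- 1/2: 0.498 × 0.502 = 0.25
- 2/3: 0.623 × 0.650 = 0.40
- 3/4: 0.676 × 0.731 = 0.49

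At d = 0.2 to 0.3 the same calculation gives 9–19%, so the size of this problem depends heavily on the assumed effect.

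**The case against.** Several objections have force and limit the point.

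- **RHR may already be covered.** The protocol's list of conventional measures is open-ended, so a reader who infers that adding RHR contradicts the protocol goes too far. The loss of laser scanning and the change of week remain.
- **The RHR hypothesis does not claim exclusivity.** The SAP says where the effect will be expressed, not that it occurs only there; the remark that an effect is observable only at elevated RHR describes an earlier study. It would be wrong to say that stratum p-values cannot support the hypothesis: a significant result at ≥ 70 bears on it as written. Regression is allowed, so an interaction term is unstated, not excluded.
- **Separate stratum tests are not certain.** The contrast between overall and stratified analysis stands in the text on secondary plasma factors. A single stratum-adjusted primary comparison is not ruled out. The 21–26% figure is conditional and should not be read as this trial's error rate.
- **The whole cohort is not self-evidently primary.** One might infer that the protocol settles on all randomised subjects. But section 3.1 removes those who cannot tolerate two tablets from further analyses, and sections 9.1 and 9.6 replace early withdrawals.
- **The figures rest on assumptions.** Correlations, stratum shares and d are not in the documents.

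None of this supplies a success rule or reconciles the two documents.

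**Conclusion.** The point holds on the text alone. The primary endpoint has three unranked measures, an undefined HRV variable, no success rule and no multiplicity control. The primary time point conflicts with the protocol's, a protocol-named primary measure is missing, and the role of the RHR strata is unresolved. This must be settled before any primary claim is made.

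The numbers show why it matters. The same plan gives a false-positive rate of about 1% or less under one unstated rule (about 2% at correlation 0.9). Under another it gives 11–14%, and 21–26% under a third. They rest on two-sided 0.05 and assumed correlations.

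The missing treatment-by-RHR estimate is advisory. It matters only if the report claims that the effect differs by RHR or is confined to ≥ 70.

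A reader might also infer from the dates that the endpoint was changed with results in view: the SAP is dated Dec 14, 2018, and the last subject was planned to finish by August 2018. The documents do not show whether unblinding had occurred and do not support that inference.

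**What to change.** Make these changes before unblinding. If unblinding has already occurred, make them and label them as post hoc.

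1. **Reconcile the documents.** Settle week 12 against week 24 and the two measure lists. Record why the time point changed, why RHR was added and whether laser scanning stays primary.
2. **Define success.** Name one HRV variable, with index and test phase. State how many primary measures must succeed, and control the error rate across the reconciled list by Holm or a fixed order.
3. **Name one primary RHR analysis.** It can be a stratum-adjusted comparison or the ≥ 70 stratum; the choice is the sponsor's. Label the others, including ≥ 80, supportive. Reconcile the analysis set with the exclusion and replacement rules in Protocol 3.1, 9.1 and 9.6.
4. **Advisory.** Rest any claim of a differing or confined effect on a treatment-by-baseline-RHR estimate with its confidence interval, not on a comparison of stratum p-values. With power of about 0.23–0.29 under the assumed inputs, it is for estimation only.

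Cost: wording in both documents and no extra subjects. At d = 0.634, Holm's first step lowers per-measure power from 0.80 to about 0.65 with three measures. The population choice is a real trade-off. If that effect exists only at ≥ 70, whole-cohort power at shares 1/2, 2/3 and 3/4 is 0.29, 0.46 and 0.56, against 0.50, 0.62 and 0.68 in the stratum. If it is uniform, whole-cohort power is 0.80 against the same stratum figures.
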